4.2 Randomization and implementation

All patients are randomly divided into the treatment group and control group at a ratio of 1:1. Central dynamic randomization is adopted so that each center is grouped in competition. The centralized random grouping program will be performed with Interactive Web-based Randomization System (IWRS) provided by the Peking University Clinical Research Institute. The main investigators have their own accession numbers and passwords to

ensure the security and integrity of the login system. After screening each eligible participant in each study center, the researchers should enter the randomized system with the account number and enter the information about the subject to obtain related drug package number. The researchers should deliver drugs according to the drug package number. Subjects are randomly assigned to the treatment and control groups according to stratification factors, and stratification factors include:

- 1. Has take thrombolytic therapy: Yes or no
- 2. NIHSS score: 4-7 points, 8-14 points and 15-22 points;

The randomization method is Pocock and Simon minimal randomization. Patients must start treatment within 24-48 hours after randomization. This study is treated with non-repetitive randomization.

4.3 Blind method and measures

4.3.1 Blind coding and storage of blind code

The biometric experts, who are independent of the statistical analysis, can use central stochastic system to randomly produce drug package number, and the random parameter cannot be modified or viewed after the start of project. The drug was coded according to the drug package number by statisticians unrelated to this study. After coding, the blind code should be sealed.

4.3.2 Emergency unblinding

In the event of a serious adverse event and in the need for emergency unblinding, the researchers in charge of center should login randomization system for emergency unblinding. If it fails unblinding due to speed or other reasons, the researchers can directly call the Peking University Clinical Research Institute by 24-hour hotline, and the system administrator will perform emergency unblinding. This unblinding process involves only the subject, not exposing grouping information of other subjects. Once the case is performed with emergency unblinding, he or she should be considered as off patient, but if there is any adverse reaction, these reactions should also be included in the analysis of adverse reactions.

4.3.3 Unblinding provisions

The study adopts twice unblinding. After blind check, the data is locked, main researchers, medical statisticians, data administrators and sponsor representatives will do the first unblinding, and the random number corresponding to the group will be marked with A or B, in order to make statistical analysis on all data. At the end of statistical analysis, summary report is completed, and then a second unblinding should be taken to determine the exact group of A and B.

4.4 Sample size

According to the China National Stroke Registry (CNSR), the patients with mRS \leq 1 at 3 months accounts for 39.59% in those with NIHSS of 4-22 at hospitalization. There is 40% of patients with mRS \leq 1 at 90 days in the control group, and 47% in the treatment group. Treatment group and control group are designed in geometric proportion. Sample size is calculated by PASS 2008 (α =0.05, two-tailed test; β =0.2, power of test=80%). A total of 787 patients are enrolled in the treatment group and control group, respectively. Considering off patients in clinical study, we add another 20% of sample size that a total of 1968 cases are included in this study. The patients are divided at a ratio of 1:1 into treatment group and control group, and the study will be carried out in 50 centers.

Study No.: Document No.:

4.5 Subjects

The enrolled patients should satisfy the following inclusion criteria, and not meet any exclusion criterion. In addition to following criteria, the patient should also be excluded if at any contraindicated medical condition or use of incompatibility drug during basic treatment period.

4.5.1 Inclusion criteria

- 1. Have onset of ischemic stroke within 72 hours, and be diagnosed by CT/MRI;
- 2. At age of 35to 75;
- 3. First onset or with past history of ischemic stroke, but have recovered before this onset, that is with mRS score <1;
- 4. With clear nervous system orientation sign, and national institutes of health stroke scale (NIHSS) ≥4 and <22:
 - 5. The patient or his (her) legal representative has signed informed consent before the start of study.

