5.1. Inclusion criteria

- 1. Ischemic stroke within 72 h after onset, confirmed by MRI or CT;
- 2. Age 35–75 years, inclusive;
- 3. Patients with the first attack or patients with stroke history (modified Rankin Scale score 0-1);
- 4. Clear signs of localization of nervous system, NIHSS score 4 to 22;
- 5. Patient or proxy has signed *Informed Consent Form*.

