4.5.2 Exclusion criteria

- 1. Head CT/MRI indicates intracranial hemorrhagic disorders: Hemorrhagic stroke, epidural hematoma, intracranial hematoma, intraventricular hemorrhage, subarachnoid hemorrhage, recurrent bleeding after cerebral hemorrhage and so on;
 - 2. Transient ischemic attack (TIA);
- 3. Serious disturbance of consciousness: the patient with 1a level of consciousness scale >1; with dysphagia and unable to take oral administration of capsules; with any of upper and lower limb motor function 5a, 5b, 6a and 6b in NIHSS >2;
 - 4. The patient with stroke that is caused by cerebral tumor, cerebral trauma, blood diseases and so on;
 - 5. Have disorders with bleeding tendency;
 - 6. Have received endovascular treatment after onset;
- 7. The one with dementia, severe Parkinson's disease, mental disorders, limb dysfunction caused by other disorders, and other diseases that may affect the judgment of efficacy;
- 8. The one with uncontrollable hypertension/ hypotension: Systolic blood pressure \geq 200mmHg or diastolic blood pressure \geq 110mmHg; or systolic blood pressure \leq 90mmHg or diastolic blood pressure \leq 60mmHg; the one with severe hyperglycemia / hypoglycemia: blood sugar \geq 400mg / dl (22.2mol / L) or \leq 50 mg / dl (2.8 mol / L);
- 9. The patient with liver dysfunction (transaminase level more than 2 times of the upper limit of normal), renal dysfunction (creatinine value more than 1.5 times of the upper limit of normal), cardiac dysfunction or other serious systemic disease, and the life expectancy \leq 3 months;
 - 10. Concomitant with malignant tumor or be taking anti-tumor treatment;
 - 11. Have past allergic history to studying drug or control drug;
- 12. The patient during pregnancy or breast feeding, or the one with possibility of pregnancy or plan to get pregnant;
 - 13. Have participated or be participating in other clinical studies in the past 3 months;
 - 14. The one with the situation that is unsuitable for enrollment by the researcher;

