6.1.2 Per-protocol set

Per-protocol set (PPS): The set that conforms to inclusion criteria, does not conform to exclusion criteria and completes therapeutic schedule. Do analysis (PP analysis) to cases that are fit to experiment program, with good compliance, not taking any prohibited drug and complete required contents of CRF.

PP population is the secondary population for curative evaluation in this study.

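### SAP 4.5.1 sets narrower eligibility limits than protocol 5.1, and SAP 6.1.2 does not say which list defines the per-protocol set

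*Combined protocol and SAP*

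**What the plan says.** Protocol 5.1, repeated in the synopsis, sets the limits under which sites enrol. Item 3 accepts a first attack or "patients with stroke history (modified Rankin Scale score 0-1"), with no restriction on the type of earlier stroke. Item 4 requires "NIHSS score 4 to 22".

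SAP 4.5.1 words the same two items differently. Item 3 accepts a first onset or a past ischemic stroke from which the patient had recovered, "that is with mRS score <1". Item 4 asks for an NIHSS of at least 4 and below 22.

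Elsewhere the SAP treats 22 as eligible. Section 4.2 stratifies by "NIHSS score: 4-7 points, 8-14 points and 15-22 points". Section 4.4 takes the control rate from registry patients with NIHSS 4-22. Section 6.2.4 and Tables 7.3.1.3 and 7.5.2.3 use a 15-22 class.

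SAP 6.1.2 defines the PPS as "The set that conforms to inclusion criteria, does not conform to exclusion criteria and completes therapeutic schedule" and calls it the secondary population for efficacy. SAP 6.1.1 makes the full analysis set (FAS) the main one. SAP 6.2.4 runs both on the primary endpoint at the same time.

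**The concern.** The SAP lists only one set of inclusion criteria, its own, and SAP 4.5 introduces it as the set that enrolled patients must meet. An analyst who builds the PPS from the SAP alone would therefore class some properly enrolled patients as eligibility violators. An analyst working from the protocol would keep them. Each could cite a text, so the PPS is not fully prespecified. It supplies a parallel analysis of the primary endpoint and a column in the main efficacy and subgroup tables, so the difference would reach reported results.

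**Working it through.** **Comparing the criteria.** Both scales take whole numbers, so each limit becomes a set of allowed values.

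| Item | Protocol 5.1 | SAP 4.5.1 | Admitted by the protocol only |
|---|---|---|---|
| mRS with an earlier stroke | 0, 1 | 0 | 1 |
| Type of earlier stroke | any | ischemic | non-ischemic |
| Baseline NIHSS | 4 to 22 | 4 to 21 | 22 |

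The second row has one caveat. If first onset in the SAP means first ischemic stroke, a patient with an earlier hemorrhagic stroke could still enter by that route. The SAP does not say.

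**Which analysis sets use the criteria.** SAP 6.1.1 defines the FAS by randomization, treatment and a post-treatment assessment. SAP 6.1.3 defines the safety set by treatment and recorded safety data. Neither refers to eligibility. Only SAP 6.1.2 does.

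**Reproducing the planned sample size.** Inputs from protocol 4.2 and SAP 4.4 are 40% against 47%, two-sided alpha 0.05, power 80%, 1:1 allocation and a 20% dropout allowance. With pooled variance and no continuity correction:

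n = [1.960 × √(2 × 0.435 × 0.565) + 0.8416 × √(0.40 × 0.60 + 0.47 × 0.53)]² / 0.07²

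= (1.3741 + 0.5886)² / 0.0049, which rounds up to 787 per arm.

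With dropout, 787 / 0.8 = 983.75, so 984 per arm and 1,968 in total. Both planned figures reproduce, and the eligibility mismatch changes neither.

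**Sensitivity of the PPS.** The documents give no count of patients with prior-stroke mRS 1, a non-ischemic earlier stroke, or NIHSS 22. The share removed, f, is therefore an assumption. So are a PPS of 787 per arm (what remains after the planned dropout) and unchanged rates of 40% and 47%.

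Power = Φ{[0.07 × √n − 1.3741] / 0.6994}, with n = 787 × (1 − f)

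| Assumed f | n per arm | Power |
|---|---|---|
| 0 | 787 | 80.0% |
| 1% | 779 | 79.6% |
| 2% | 771 | 79.2% |
| 5% | 748 | 78.0% |
| 10% | 708 | 75.8% |

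The loss is about 0.4 percentage points for each 1% removed.

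**The case against.** **The limits may be a transcription fault.** Adding the missing bar to each less-than sign restores the protocol limits exactly. The SAP's repeated use of 22 as an eligible score suggests that the narrower NIHSS limit was not intended. This stands as a likely cause, and the source page should be checked. It does not explain the added ischemic restriction, which is in words. Other inequality signs survive in the SAP, including one on the same line.

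**SAP 6.1.2 does not point to SAP 4.5.1.** Protocol 13.3 places the eligibility check at blind review, and protocol section 14 binds all parties to the approved protocol. This also stands. A reader might infer that these patients will certainly be dropped, but the documents support only a conditional statement. If blind review uses the protocol list, nobody is lost this way.

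**No variable is named for the filter.** The visit schedules list mRS at screening, and SAP Table 7.2.1.2 records only first onset or recurrence. Neither names a pre-stroke mRS. This makes an automatic exclusion on that item less likely, but a manual eligibility review could still apply it.

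**The impact is limited.** The PPS is secondary. These features are fixed before randomization, so removal would fall on both arms alike. A reader might infer a biased treatment difference, and the documents do not support that. NIHSS 22 may also be rare, because exclusion 3 caps item 1a at 1 and each limb item at 2.

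**Conclusion.** The point holds in conditional form. The SAP's eligibility list is narrower than the protocol's and conflicts with the SAP's own strata, tables and sample-size source. Following the SAP as written would remove correctly enrolled patients from the PPS. The effect is a changed population and lower precision in a secondary set. The FAS, the safety set and the planned 787 per arm and 1,968 in total are unaffected. The power cost of about 0.4 points per 1% removed rests on the assumed PPS of 787 per arm and unchanged response rates.

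Three stronger readings should be avoided:

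- **A headcount.** A reader might guess that 20-30% have an earlier stroke and 20-40% of those have mRS 1. That gives 0.20 × 0.20 × 1,968 = 79 to 0.30 × 0.40 × 1,968 = 236 patients. Nothing in the documents anchors those shares, and 1,968 is the randomized total, not a set of treatment completers.
- **A higher PPS success rate.** A reader might argue that prior-stroke mRS 1 leaves little room for success. The documents do not show this. A patient who returns to mRS 1 counts as a success, and Appendix 2 of the protocol counts only symptoms since the stroke.
- **A further PPS loss through exclusion 1.** The hemorrhage wording differs, but SAP 4.5.2 covers intracranial hemorrhagic disorders generally and its list is open-ended. No effect on the PPS is shown.

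This should be corrected. It concerns a secondary population, but the rule as written is wrong and costs almost nothing to repair.

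**What to change.** 1. Check SAP 4.5.1 against the source page for lost signs in items 3 and 4.
2. Align those items with protocol 5.1, including the type of earlier stroke.
3. Add one sentence to SAP 6.1.2 stating that PPS eligibility is judged against the protocol criteria in force at enrolment.
4. Reconcile the hemorrhage exclusion across the synopsis, protocol 5.2 and SAP 4.5.2. The protocol names bleeding that follows an infarct, while the SAP has "recurrent bleeding after cerebral hemorrhage and so on". Do not copy protocol 5.2 item 1 as it stands. It names head CT only, whereas the synopsis and the SAP also name MRI, so copying it would create a new mismatch.
5. Before unblinding, count the patients with prior-stroke mRS 1 (if recorded), an earlier non-ischemic stroke, or NIHSS 22. That replaces the assumed range with a figure.

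The cost is a wording change to the SAP before blind review and one blinded tabulation. Neither the sample size nor the primary analysis changes.

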4.5.2 Exclusion criteria

- 1. Head CT/MRI indicates intracranial hemorrhagic disorders: Hemorrhagic stroke, epidural hematoma, intracranial hematoma, intraventricular hemorrhage, subarachnoid hemorrhage, recurrent bleeding after cerebral hemorrhage and so on;
 - 2. Transient ischemic attack (TIA);
- 3. Serious disturbance of consciousness: the patient with 1a level of consciousness scale >1; with dysphagia and unable to take oral administration of capsules; with any of upper and lower limb motor function 5a, 5b, 6a and 6b in NIHSS >2;
 - 4. The patient with stroke that is caused by cerebral tumor, cerebral trauma, blood diseases and so on;
 - 5. Have disorders with bleeding tendency;
 - 6. Have received endovascular treatment after onset;
- 7. The one with dementia, severe Parkinson's disease, mental disorders, limb dysfunction caused by other disorders, and other diseases that may affect the judgment of efficacy;
- 8. The one with uncontrollable hypertension/ hypotension: Systolic blood pressure \geq 200mmHg or diastolic blood pressure \geq 110mmHg; or systolic blood pressure \leq 90mmHg or diastolic blood pressure \leq 60mmHg; the one with severe hyperglycemia / hypoglycemia: blood sugar \geq 400mg / dl (22.2mol / L) or \leq 50 mg / dl (2.8 mol / L);
- 9. The patient with liver dysfunction (transaminase level more than 2 times of the upper limit of normal), renal dysfunction (creatinine value more than 1.5 times of the upper limit of normal), cardiac dysfunction or other serious systemic disease, and the life expectancy \leq 3 months;
 - 10. Concomitant with malignant tumor or be taking anti-tumor treatment;
 - 11. Have past allergic history to studying drug or control drug;
- 12. The patient during pregnancy or breast feeding, or the one with possibility of pregnancy or plan to get pregnant;
 - 13. Have participated or be participating in other clinical studies in the past 3 months;
 - 14. The one with the situation that is unsuitable for enrollment by the researcher;

4.5.3 Fall off (withdraw) standard

The subject, who has signed the informed consent and screened eligibly for the study, can be regarded as drop out case if withdraw from the program for any reason and do not complete the programme.

The patient has the right to withdraw from the study at any time for any reason. The researcher is also entitled to exclude the patient if he has a disease, an adverse event or violates the study protocol, or due to management reason or other reason. It should avoid any unnecessary withdrawal, and actively take measures to complete the final test as much as possible for the efficacy and safety of analysis. However, when the patient

decides to withdraw, the researcher should contact the patient or his / her relatives by phone or personal interview, and as far as possible confirm the reason for the withdrawal. The researcher should recover the remaining drug when the patient withdraws, finish the final assessment, complete the case report as much as possible, explain the cause of withdrawal and take follow-up on the endpoint. If the cause of withdrawal is an adverse event, the main event should be recorded in the study medical record.

Common reasons to withdraw from the study: Adverse events, lack of efficacy, taking endovascular treatment during follow-up period, violation of research programme (including poor compliance), loss of follow-up (including withdrawal due to patient's own reason), incomplete study decided by the sponsor after the judgement of researchers and other reasons;

4.5.4 Standards for suspending the study

- 1. Having allergic reaction clearly associated with study drugs;
- 2. Having adverse symptoms and signs definitely associated with study drugs, abnormal findings, or conditions in need of ending the study after judgment of researchers, which are clearly related to the medicine under study;
 - 3. Female subjects get pregnant during the study;
 - 4. The patients ask to end further study;
 - 5. Take endovascular treatment during study period;
- 6. If there is occurrence of vascular events, it should be determined as appropriate: Discontinue study drug and terminate study, if the patient has hemorrhagic stroke, and the related condition should be recorded in appropriate part of medical records. If there is occurrence of TIA/ ischemic stroke/ myocardial infarction, the subjects do not need to discontinue taking study drug or withdraw from the study, only if concomitant drugs contraindicated by the study need to be taken.

5. Evaluation index

5.1 Primary effect index

Improvement of daily life ability 90 days after treatment (ratio of mRS score ≤1)

5.2 Secondary effect index

1. Improvement of neurological deficits (ratio of NIHSS≤1 or improve 4 score or more);

Improvement of neurological deficits (ratio of NIHSS≤1 or improve 4 score or more): It is effective for NIHSS≤1 or reducing 4 points or more; compare the ratio of efficacy and inefficacy and the continuous change of NIHSS between treatment group and control group 90 days after random treatment;

2. Improvement of daily life ability (ratio of BI index ≥85);

Ratio of patients with BI index≥85: BI score≥85 indicates the patient with ability of independent living; compare the ratio of patient with ability of independent living and continuous change of BI between treatment group and control group at 90 days after random treatment;

3. Disability rate (ratio of mRS score \geq 3)

mRS≥3 indicates the patient without self-care ability; compare the disability rate between treatment group and control group at 90 days after random treatment;

4. Continuous change of mRS score

Compare change of mRS score at baseline, 7d, discharge day and 90d between treatment group and control group;

5. Incidence of ischemic cerebrovascular diseases during follow-up period;

Ratio of ischemic stroke or TIA within 90 days after random treatment, or ratio of new ischemic focus detected by MRI during the last visit, and take this kind of patients as a group for evaluation or respective evaluation:

6. Incidence of combined vascular events during follow-up period;

Accumulated ratio of patients having newly combined vascular events within 90 days after random treatment;

Definition of combined vascular events: Include any type of stroke (ischemic stroke and hemorrhagic stroke), TIA, myocardial infarction and vascular death.

Vascular death: Hemorrhagic death or fatal pulmonary embolism of any organ.

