Abbreviations	Interpretation
AE	(Adverse Event)
ALT	Alanine aminotransferase
AST	Aspartate aminotransferase
BUN	Urea nitrogen
CI	(Confidence Interval)
Cm	Centimeter
CMH	Cochran-Mantel-Haenszel Cochran-Mantel-Haenszel test
Cr	Creatinine
CRF	Case report form
CRO	Contract research organization
DRQ	DRQ
F	F-statistics (results of covariance analysis)
FAS	(Full Analysis Set)
GCP	Good Clinical Practice
ITT	Intentionality (population)
LOCF	(Last Observation Carried Forward)
Max	Maximum value
Mean	Mean
Median	Median
Min	Minimal value
P	P value
Power	Power of test
PP	Per-protocol (population)
PPS	Per-protocol Set
SAE	Serious Adverse Event
SD	Standard Deviation
SOP	Standard operating procedure
SS	Safety set

2. Study title

A randomized, double-blind, placebo controlled evaluation, multicenter clinical study of Tongxinluo Capsule in ischemic stroke patients

3. Study objectives

The primary objective of this study: In comparison with placebo, to evaluate the improvement of self-help ability of patient's daily living after early application of Tongxinluo Capsule with treating ischemic stroke (within 72 hours after onset) for 90 days.

The secondary objective of this study: To investigate the improvement of neurologic impairment and self-help ability of patient's daily living, differences of disability rate, incidence of combined vascular events and incidence of ischemic cerebrovascular diseases, and safety of medication between placebo and early application of Tongxinluo Capsule with treating ischemic stroke (within 72 hours after onset) for 90 days. To evaluate the safety and effectiveness of Tongxinluo Capsule at different etiological typing and randomized times, and in different imaging subgroup analyses and more exploratory analyses.

4. Study design

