6.2.4 Efficiency evaluation

Baseline efficiency: Describe the baseline of each curative index, and comparison between groups should be made in accordance with general condition. Modified Rankin (mRS) score is regarded as ranked data, and should be compared with Wilcoxon rank sum test. NIHSS score should be regarded as quantitative data and ranked data (4-7 points, 8-14 points and 15-22 points) for description and comparison; BI score as quantitative data and enumeration data (<85 points, ≥85 points) for description and comparison.

Primary efficiency indexes:

PP analysis and FAS analysis should be performed at the same time; evaluation on patients with modified Rankin (mRS) score≤1 should be mainly conducted ontaken at day 90 day (PP set) and the time for suspending and drop-out (FAS set). Primary indexes should be compared between the two groups with CMH-γ2 method for controlling central effect.

Superiority test is adopted for primary indexes, and the hypotheses under test are as follows:

$$H_0$$
: $\pi_{\text{treatment group}} - \pi_{\text{control group}} \le 0$

$$H_1: \pi_{\text{treatment group}} - \pi_{\text{control group}} > 0$$

$$\alpha = 0.025_{\text{(one-sided)}}$$

The treatment group is superior to control group, if H0 is rejected under α level, or lower limit of 95% Cl for difference of retention rate between the two groups is higher than 0. Take sensitivity analysis on primary efficiency indexes with modified Rankin (mRS) score≤2 points as the limit.

Other secondary indexes can be statistically analyzed in accordance with methods for primary indexes.

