7.3.3 Secondary effect index - Improvement of neurological deficit

Table 7.3..3.1 Improvement of neurological deficits at 90 days after treatment

		FAS		PPS	
		Treatment		Treatment	
Item	Index	group	Control group	group	Control group
Improvement of neurological	Efficiency n(%)				
deficits at 90 days after	Inefficiency				
treatment	n(%)				
	Missing				
	Statistics				
	P value				

Note: It is effective for NIHSS score ≤ 1 or reducing 4 points or more

Table 7.3.3.2 Continuous change of NIHSS score at 90 days after treatment (FAS)

Item	Index	Treatment group	Control group	
	N(Missing)			
Baseline NIHSS score	Mean(SD)			
	Median			
	Q1,Q3			
	Min, Max			
	Statistics			
	P value			
	N(Missing)			
NIHSS score at 90 days after treatmen	t Mean(SD)			
	Median			
	Q1,Q3			
	Min, Max			
	Statistics			
	P value			
Change of NIHSS score at 90 days	N(Missing)			
after treatment comparing with that at baseline	Mean(SD)			
	Median			
	Q1,Q3			
	Min, Max			
	Statistics			
	P value			
	95%CI			
	Statistics			
	P value			

Table 7.3.3.3 Continuous change of NIHSS score at 90 days after treatment

The same as above

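### The supporting full-scale NIHSS and Barthel comparisons at Day 90 have no stated baseline adjustment, although baseline scores are collected; adjusting would gain precision at almost no cost

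*Combined protocol and SAP*

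**What the plan says.** SAP 5.2 attaches a full-scale comparison to each of two responder outcomes. For NIHSS (responder: score of 1 or less, or a fall of at least 4) the instruction is to "compare the ratio of efficacy and inefficacy and the continuous change of NIHSS between treatment group and control group 90 days after random treatment". For BI (responder: 85 or more) it is to "compare the ratio of patient with ability of independent living and continuous change of BI between treatment group and control group" at 90 days. Protocol 9.1.2 says the same.

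The shell for NIHSS, SAP Table 7.3.3.2, has three blocks: baseline, Day 90, and the "change of NIHSS score at 90 days" relative to baseline. Each block has a statistic and a P value. The change block has a 95% CI and a second statistic and P value. No row is labelled as an adjusted difference. The BI shell (Table 7.3.4.2) is given only by a cross-reference to Table 7.4.2.2, a vital-sign table with the same kind of baseline, Day-90 and change rows.

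On method, SAP 6.2.1 names a t test (worded as paired) or a Wilcoxon rank-sum test for quantitative data, in its rule for comparing general characteristics. SAP 6.2.4 adds: "Other secondary indexes can be statistically analyzed in accordance with methods for primary indexes". The primary method is a CMH test controlling for centre only.

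Covariance analysis appears once, in the SAP's list of abbreviations and statistics, where F is glossed as "F-statistics (results of covariance analysis". No analysis section refers to it.

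Baseline NIHSS, mRS and BI are all assessed at Visit 1 (protocol 8.1). NIHSS band (4-7, 8-14, 15-22) is a minimisation factor; BI is not.

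**The concern.** Eligibility allows NIHSS from 4 to 22, so the most a patient can improve depends on where that patient started. A raw change score keeps this variation in its standard error, and a raw Day-90 score keeps whatever part of the Day-90 variation the baseline predicts. A model that conditions on baseline removes it. Without adjustment, confidence intervals for the full-scale effect on neurological deficit and daily living are wider than the data require, and a real effect is more likely to be missed. The SAP also leaves the role of covariance analysis open. If that is settled after the data are seen, it becomes a post hoc choice.

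**Working it through.** **The plan's own figure.** SAP 4.4 assumes "There is 40% of patients with mRS" of 1 or less in the control arm and "47% in the treatment group", with α = 0.05, "two-tailed test; β =0.2, power of test=80"%. The pooled two-proportion formula, with mean proportion 0.435, is

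n = [1.96·√(2·0.435·0.565) + 0.8416·√(0.40·0.60 + 0.47·0.53)]² / 0.07² = 786.2, rounded up to 787 per arm.

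Then 787/(1 − 0.20) = 984 per arm, or 1,968 in total. Both figures reproduce. They concern the primary endpoint; the documents state no power for NIHSS or BI on the full scale.

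**Inputs that must be assumed.** Let r be the correlation between baseline and Day-90 scores and k the ratio of Day-90 SD to baseline SD. Neither is in the documents, so a range is shown. Set the baseline SD to 1.

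**Per-patient variance of each between-arm comparison:**

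- raw change: V_change = 1 + k² − 2rk
- raw Day-90 score: V_day90 = k²
- Day-90 score adjusted for baseline: V_adj = k²(1 − r²)

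The differences are V_change − V_adj = (1 − rk)² and V_day90 − V_adj = r²k². Neither can be negative. The first is zero only when the slope of Day 90 on baseline, rk, equals 1; the second only when r = 0. So in large samples adjustment is never worse than either planned test.

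**Power.** Fix the effect at which the raw-change test has 80% power (1.96 + 0.8416 = 2.8016). A test with variance ratio R to the change test then has power Φ(2.8016/√R − 1.96). For equal SDs (k = 1):

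| r | V_change | V_adj | V_adj/V_change | Change test | Day-90 test | Adjusted |
|---|---|---|---|---|---|---|
| 0.3 | 1.40 | 0.91 | 0.65 | 80% | 91% | 93.5% |
| 0.5 | 1.00 | 0.75 | 0.75 | 80% | 80% | 89.9% |
| 0.7 | 0.60 | 0.51 | 0.85 | 80% | 58% | 86.0% |
| 0.8 | 0.40 | 0.36 | 0.90 | 80% | 43% | 84.0% |

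The Day-90 column uses R = 1/V_change. At r = 0.3, for example, R = 1/1.40 = 0.714 and the power is Φ(2.8016/0.845 − 1.96) = Φ(1.355) = 91%.

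In patient numbers, to match the adjusted analysis on 787 per arm the change test would need 787 × V_change/V_adj, which is 1,211, 1,049, 926 and 874 per arm at these four correlations.

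**Unequal SDs:**

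- k = 0.8, r = 0.3: adjusted 97.7%, Day-90 test 96.5%.
- k = 0.8, r = 0.5: variance ratio to change 0.48/0.84 = 0.571; adjusted 96.0%, Day-90 test 89%.
- k = 1.2, r = 0.5: variance ratio 1.08/1.24 = 0.871; adjusted 85.1%.
- k = 1.2, r = 0.8: slope 0.96, variance ratio 0.5184/0.52 = 0.997; adjusted 80.1%, so almost no gain over change.

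These formulas describe comparisons of means (the t-test option). The same direction is expected for the rank-sum option, but its size was not computed.

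**The case against.** **The full scale is not tested only as raw change.** Table 7.3.3.2 also has a statistic and P value for the Day-90 score. This stands, and it matters: at r = 0.3 most of the apparent gain over change is already available from the Day-90 test (91% against 93.5% for k = 1; 96.5% against 97.7% for k = 0.8). The Day-90 test then falls well behind as r rises.

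**Absence of adjustment is inferred from silence.** The change block has two unnamed statistics, and the abbreviation list defines an F from covariance analysis, so one of them might be that F. It is fair that the shells name no test. But SAP 6.2.5 describes both a before-after and a between-group comparison for the vital signs, whose shell has the same layout, and that is the more natural reading of the two pairs. The abbreviation entry does not supply an adjustment. The general rule in SAP 6.2.1 also sits under comparison of general characteristics, and SAP 6.2.4 is permissive, so the between-arm method for these tables is loosely specified in any case.

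**These are supporting analyses.** The synopsis and protocol 7.1.2 list only the NIHSS and BI proportions. The full-scale comparisons are additions within those items and are not powered. This stands and limits the weight of the point.

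**Imbalance is unlikely to be a problem.** A reader might infer that the unadjusted comparison is biased. The documents do not support that: allocation is randomised, NIHSS band is a minimisation factor, and the planned arms have 984 patients each. Minimisation does not, however, take baseline variation out of the standard error of an unadjusted test.

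**Conclusion.** The point holds as a matter of efficiency. No stated method for the full-scale NIHSS and BI comparisons uses the baseline score, and adjusting for it would be at least as precise in large samples as either unadjusted test in the shell. With equal SDs and r from 0.3 to 0.8, both assumed, the variance falls to 65% to 90% of the change-score variance, and 80% power becomes about 93.5% to 84%. The true gain cannot be fixed from the documents and could be close to nil against raw change.

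It would go too far to conclude that the trial is underpowered or that its main result is at risk: the primary endpoint, its sample size and the responder outcomes are unaffected. This is a change that should be made, not one on which the validity of the trial depends.

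**What to change.** In SAP 6.2.4 and in Tables 7.3.3.2-7.3.3.3 and 7.3.4.2-7.3.4.3, make the between-arm inference a covariance analysis of the Day-90 score. The terms are treatment, the baseline value of the same scale, and the minimisation factors (thrombolysis and NIHSS band); centre may be added. Prespecify a rank-based or proportional-odds version, with the rule for using it, for skewed or ceiling-limited scores. Report the adjusted difference with its 95% CI. Keep the raw change and Day-90 rows as description, and leave the responder proportions as planned. Tie the covariance-analysis entry in the abbreviation list to this model, and give the BI tables their own shell in place of the pointer to a vital-sign table.

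The cost is SAP wording and one model per table, settled before the first unblinding. It needs no new data, visits or patients. The small downside is a modelling assumption, which the rank-based or proportional-odds version covers.
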